4.1 Rationale for Subject Selection

Subjects of any gender will be considered for inclusion in this study. There will be no racial, ethnic, or gender discrimination. Persons in jail or prison are not eligible for this study (see 4.3.2). Pregnant and breastfeeding women will not be eligible (see section 4.3.1).

4.2 Subject Inclusion Criteria

To be eligible for participation on this protocol, a participant must satisfy all of the following conditions:

1. Age ≥ 18 years old
2. Able and willing to sign informed consent

3. Chronically infected with HCV (any genotype), defined as any individual with documentation of positive HCV antibody and positive HCV RNA test (HCV RNA of 2,000 IU/mL or greater)
4. If HIV+, suppressed on a stable, protocol-approved, ARV regimen for \geq 8 weeks prior to enrolling in the study
 - a. HIV RNA $<$ 50 copies/mL (or $<$ LLOQ if the local laboratory assay's LLOQ is \geq 50 copies/mL) prior to Screening. Subjects with an isolated or unconfirmed HIV RNA $>$ 50 copies/mL (or $>$ LLOQ if the local laboratory assay's LLOQ is \geq 50 copies/mL) are not excluded.
 - b. CD4 count $>$ 100 cells/mm³
5. Willing to have samples stored for future use
6. If tested positive for NS5A resistance-associated polymorphisms or PEG-IFN and ribavirin experienced, able to tolerate ribavirin-containing regimen for 16 weeks. Ribavirin will be administered at the discretion of the PI.
7. Women of childbearing potential who receive ribavirin will have to be willing to commit to abstinence from sexual activity, or use of two forms of contraceptive during treatment and for the 6 months after completion of ribavirin. Men receiving ribavirin who are sexually active with women will also have to be willing to commit to abstinence from sexual activity, or use of two forms of contraceptive during treatment and for the 6 months after completion of ribavirin.

4.3 Subject Exclusion Criteria

A participant will be ineligible to participate in this study if any of the following criteria are met:

1. Decompensated liver disease (Childs Pugh B or C)
2. Unable to comply with research study visits
3. Poor venous access not allowing screening laboratory collection
4. Have any condition that the investigator considers a contraindication to study participation
5. Pregnant or breastfeeding woman
6. Prior HCV treatment with Direct-Acting Antivirals. Note: Patients who are treatment-experienced with PEG-IFN/RBV will not be excluded; their inclusion in the study will be considered by the PI.
7. HIV+ patients with prior HCV treatment who achieved sustained virologic response (SVR)/ functional cure
8. Use of a concomitant medication that is contraindicated with the use of the DAA for HCV treatment (per package insert)
9. Coinfection with HCV and HBV, in particular HBsAg + patients.
 - a. Patients with HBcAb+ will not be excluded, but will have HBV DNA levels checked and will be monitored while on DAA therapy and medically managed as considered appropriate by the PI.
10. Have any condition that the investigator considers a contraindication to study participation or not eligible per standard of care for HCV treatment

11. Patients with the following devices are excluded from participating in the cardiovascular MRI study:

- Central nervous system aneurysm clip
- Implanted neural stimulator
- Implanted cardiac pacemaker or defibrillator
- Cochlear implant
- Ocular foreign body (e.g. metal shavings)
- Implanted insulin pump
- Metal shrapnel or bullet

12. The following groups of people are also excluded from participating in the cardiovascular MRI study:

- Patients with stable renal disease (estimated glomerular filtration rate (eGFR)<30ml/min/1.73m² body surface area. The eGFR must be within two weeks of the the MRI exam.
- Patients with acute renal disease.

13. Patients who choose to have the cardiac MRI and are over 60 years of age, have a history of renal failure, or have type I or II diabetes mellitus must have laboratory tests the same day as the MRI exam.

14. Positive urine drug screen at screening. Not all patients with positive drug screen will be excluded; decision will be made by the PI.

4.3.1 Justification for Exclusion

Pregnancy: Pregnant women are excluded from this study per FDA guidance, as there are no studies of DAAs in pregnant women, and no DAA is currently FDA approved for use in pregnant women.

Breastfeeding: Breastfeeding women are excluded from this study per FDA guidance as there are no studies of DAAs in lactating women, and no DAA is currently FDA approved for use in lactating women.

Exclusion of Children: Safety and effectiveness of DAAs have not been established in pediatric patients, and as such subjects 18 years of age or younger will be excluded from the study. Because insufficient data regarding dosing or adverse events (AEs) are available in adults to judge the potential risk in children, this study poses greater than minimal risk and does not meet the Department of Health and Human Services guideline 45 Code of Federal Regulations (CFR) 46, subpart D, governing the participation of children in research.

4.3.2 Incarcerated Participants

Participants who become incarcerated during the course of the study may have to be withdrawn; continued collection of data from incarcerated subjects would be on a case-by-case basis after consultation with the IRB.

5 INTERVENTIONS

5.1 Concomitant Medications and Procedures

All concomitant prescription and over the counter medications taken during study participation will be recorded. For this protocol, a prescription medication is defined as a medication that can be prescribed only by a properly authorized/licensed clinician.

1.2 Prohibited Medications

Contraindicated medications will be determined per the package insert of the DAA, per standard of care.

6 Study Schedule

Study visits, including screening, will occur at the Center for Infectious Diseases (CID) or Drug Treatment Center (DTC) at the University of Maryland, or a Unity Healthcare clinic, based upon scheduling availability to accommodate each treatment group. The research coordinators will also oversee research operations in the clinics. See Appendix B for a detailed Study Schedule.

All phlebotomy related to the study will be done by a phlebotomist working in the clinic or clinic staff. All laboratory studies related to standard of care will be performed as per the standard practice at the site. All blood samples for storage for research will be couriered to the IHV lab.

All Cardiac MRIs will be performed at the National Institutes of Health (NIH).

Participants will be given a calendar of scheduled study visits and will be informed that any clinic visits outside of scheduled study visits may be either unscheduled visits or non-study visits. Subjects will receive this information when given the visit calendar.

Participants who are no-show for visits will be contacted as per the standard procedure for missed visits at each clinic site.

6.1 Screening /Enrollment

Screening will occur at the collocated HCV clinics at the University of Maryland Institutes of Human Virology, CID or DTC, and the Unity Healthcare Center. Subjects who meet inclusion criteria and who consent to the study will be enrolled. Outside labs performed within the last 6 months may be used to determine eligibility. Women of childbearing potential will have a pregnancy test at screening visit. All screeners will submit a urine drug screen.

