3.2 Study drugs

Direct Acting Antivirals (DAAs): For the treatment of chronic HCV, patients will be treated with one of the following FDA-approved fixed-dose combination products : Elbasvir/Grazoprevir (Zepatier), Sofosbuvir/Ledipasvir (Harvoni), Sofosbuvir/Velpatasvir (Epclusa), Glecaprevir/Pibrentasvir (Mavyret), Sofosbuvir/Velpatasvir/Voxilaprevir (Vosevi). Some of these medications require administration of concomitant ribavirin. Medication regimens will be administered as standard of care per the AASLD/IDSA HCV Treatment Guidelines. Common side effects (those that occurred in more than 5% of the patients in clinical trials) of these medications are listed below:

Elbasvir/Grazoprevir (Zepatier):

- Fatigue
- Headache

Sofosbuvir/Ledipasvir (Harvoni):

- Fatigue
- Headache
- Nausea
- Diarrhea
- Insomnia

Sofosbuvir/Velpatasvir (Epclusa):

- Headache
- Fatigue
- Nausea
- Insomnia
- Lack of energy

Glecaprevir/Pibrentasvir (Mavyret):

- Headache
- Fatigue
- Nausea
- Diarrhea

Sofosbuvir/Velpatasvir/Voxilaprevir (Vosevi):

- Headache
- Fatigue
- Diarrhea
- Nausea
- Insomnia
- Lack of energy

Ribavirin - Women of childbearing potential who receive ribavirin **must** commit to abstinence from sexual activity, or use two forms of contraception during treatment and for the 6 months after completion of ribavirin. Men receiving ribavirin who are sexually active with women **must** commit to abstinence from sexual activity, or they and their partner must use two forms of contraception during treatment and for the 6 months after completion of ribavirin. The most common side effects (occurring more than 5% of the time in clinical trials) are:

- Fatigue
- Lack of energy
- Body aches
- Fever
- Headache
- Anemia

- Rash

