6.2 Interim Visit

Up to 36 patients (12 from each group) will have a cardiac MRI performed at the NIH after screening but before Day 0 (the start of HCV treatment). See Appendix C for MRI procedure and specific inclusion and exclusion criteria.

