6.4 Study procedures – HCV treatment

During HCV treatment and in the follow-up period, patients with HCV will undergo monitoring for treatment adherence and safety per Standard of Care. Laboratory parameters and imaging used as part of the study endpoints are listed below. See Appendix B Study Schedule.

Cholesterol measurements

Patients' total cholesterol and LDL cholesterol will be obtained at screening and week 72 for cardiac risk calculations.

Cardiac biomarker and systemic inflammation assessment

For all participants, labs will be drawn at screening, week 24, and week 72: high sensitivity CRP (hSCRP), high sensitivity TRP (hsTRP), soluble markers of inflammation (IFN- γ , TNF- α , IL-6, CXCL9, CXCL10, CXCL11) and activated and exhausted naïve and memory T cells (percent of CD8+ and CD4+ T-cells which are HLA-DR+, CD38+, Tim-3+, or PD-1+).

Cardiac MRI

A subset of patients will undergo cardiac MRI; up to 12 patients will be recruited from each of the three groups to undergo cardiac MRI at the NIH clinical center at Day -7 (interim visit) and week 72. Patients who are claustrophobic or cannot tolerate the MRI procedure will not be selected for this portion of the study. Cardiac MRI will be utilized to assess changes in myocardial injury, degree of post-contrast enhancement, T1 mapping, and the function of the myocardium. See Appendix C for more details.

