APPENDIX C: Cardiac MRI

Introduction and MRI Procedure

Cardiovascular magnetic resonance imaging (MRI) is an excellent imaging modality capable of assessing cardiac anatomy, myocardial function, myocardial infarction/fibrosis, as well as many other types of myocardial diseases. Patients infected with the hepatitis C virus are at increased risk of cardiovascular disease. Cardiac MRI can be used to assess for epicardial coronary artery plaque, sequela of epicardial coronary artery disease, such as myocardial infarction, as well as microvascular disease.

Each patient participating in the MRI scan will receive an oral and written explanation of the purposes, procedures, and risks of this study in language appropriate for the individual's level of understanding.

All cardiac MRI scans for this study will be performed on an FDA approved 3.0T or 1.5T scanner (Aera - Siemens Healthcare, Erlangen, Germany). The radiofrequency power levels (SAR limits) will be kept within the FDA established limits. A body coil will be used during the exam. A body coil is a noninvasive device external to the body that acts as antennae to receive radiofrequency signals out of the body. The body coil used during the MRI exam will follow FDA parameters.

For the cardiovascular MRI exam, patients will receive an intravenous injection of gadolinium chelate (Gadavist, 0.15 mmol/kg) via an MRI compatible power injector.

Inclusion Criteria for the Cardiovascular MRI

18 years of age or older

Written informed consent

Exclusion Criteria for the Cardiovascular MRI

Patients with the following devices are excluded from participating in the cardiovascular MRI study:

- Central nervous system aneurysm clip
- Implanted neural stimulator
- Implanted cardiac pacemaker or defibrillator
- Cochlear implant
- Ocular foreign body (e.g. metal shavings)
- Implanted insulin pump
- Metal shrapnel or bullet

The following groups of people are excluded:

- Pregnant women
- Lactating women unless they are willing to discard breast milk for 24 hours after receiving gadolinium
- Patients with stable renal disease (estimated glomerular filtration rate (eGFR) < 30ml/min/1.73 m² body surface area). The eGFR must be within 2 weeks of the MRI exam. Patients who are over 60 years of age, have a history of renal failure, or have type I or II diabetes mellitus must have laboratories the same day as the MRI exam.

- Patients with acute renal disease.

Monitoring Patients during the Cardiovascular MRI scan

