The cardiovascular MRI exam is expected to last 60 to 90 minutes in duration. The MRI technologist will monitor the exam. Monitoring includes continuous ECG-gating. Blood pressure and pulse oximetry will be measured if clinically indicated. Patients may elect to withdraw from the MRI scan at any point.

Benefits/Risks of the Cardiovascular MRI

The cardiovascular MRI exam with gadolinium contrast involves greater than minimal risk, however may be of direct benefit to the individual patients [45 CFR 46.102(i)]. A clinical report of the exam will be available for the patients' physician.

MRI does not use ionizing radiation, and is extremely safe on a properly screened population. There is potential risk related to the magnetic field strength in patients with implanted metal devices (cochlear implants, etc), resulting in movement of these objects and subsequent harm to the patients. Patients will be screened for these objects (see exclusion criteria above) and excluded if they meet any of the exclusion criteria.

Peripheral nerve stimulation is unlikely to occur with our imaging parameters. It occurs when the magnetic field gradient switch occurs so fast that it results in peripheral nerve depolarization. The patient may feel a twitch or possibly some pain. Patient education as well as audio feedback from the patient during the exam will be used for the issue of possible peripheral nerve stimulation.

The scanner is operated within FDA guidelines for radiofrequency power levels. However, there is a small chance that a damaged or dysfunctional coil could cause some local warming in the body. Thus, for safety purposes, we ask all patients to report this sensation so we can modify scans and also verify the integrity of the hardware.

Gadolinium Administration for the Cardiovascular MRI exam

Patients must have an IV placed for gadolinium administration. Potential risks of IV placement include discomfort, bruising/bleeding, and vasovagal reactions.

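### The only pregnancy test specified is at screening: no maximum interval ties it to the Day -7 gadolinium MRI, and no repeat is specified before the week-72 gadolinium MRI

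*Combined protocol and SAP*

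**What the plan says.** **Exclusion.** Pregnancy is an exclusion for the whole study (section 4.3, criterion 5). Appendix C lists "Pregnant women" again among those who may not have the cardiac MRI. Neither place says how or when pregnancy is to be ruled out.

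**Test.** Section 6.1 states: "Women of childbearing potential will have a pregnancy test at screening visit". No other section specifies a pregnancy test. Appendix B, as it appears in the reviewed text, has no pregnancy-test row at any visit.

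**Scans.** Section 6.2 places the first MRI "after screening but before Day 0". Section 6.4 has up to 12 patients per group "undergo cardiac MRI at the NIH clinical center at Day -7 (interim visit) and week 72". Appendix C specifies intravenous gadolinium contrast for the exam, and section 7.1 classes the MRI as greater than minimal risk.

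**Renal function, for comparison.** For the kidney exclusion Appendix C adds a time limit: "The eGFR must be within 2 weeks of the MRI exam". Patients over 60, or with a history of renal failure or diabetes, "must have laboratories the same day as the MRI exam". Section 4.3, criteria 12 and 13, repeats both rules.

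**Pregnancy during the study.** Section 10 discontinues a participant who becomes pregnant. It schedules no test that would reveal the pregnancy.

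**The concern.** Pregnancy status can change between screening and either scan, and a pregnancy may not be recognised when the woman arrives for imaging. An exclusion of this kind works only if someone checks it close to the procedure. For kidney function, which can also change, the protocol sets such a check; for pregnancy it does not.

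A site could follow the written schedule exactly and give contrast at week 72 to a woman whose last required pregnancy test was about 17 months earlier. At stake is the protection of a small number of participants in an optional research scan. The standard applied is the protocol's own decision to keep pregnant women out of the scanner. No size of fetal risk is claimed here.

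**Working it through.** The plan gives no figure to reproduce. The check is calendar arithmetic on the visit schedule and a comparison of sections.

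**Inputs**
- Pregnancy test: screening visit (6.1).
- First MRI: after screening and before Day 0 (6.2), nominally Day -7 (6.4, Appendix B).
- Second MRI: week 72 (6.4, Appendix B).
- MRI participants: up to 12 in each of 3 groups (6.2, 6.4).
- Renal window: 2 weeks, or same day for higher-risk patients (Appendix C).

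**Interval from test to first scan.** The test comes first, because the MRI follows screening. No upper limit is stated, so the interval cannot be bounded from the text.

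**Interval from test to second scan**
- Day 0 to week 72: 72 × 7 = 504 days.
- Screening falls on or before the nominal Day -7, so add at least 7 days: 504 + 7 = 511 days.
- 511 / 7 = 73 weeks; 511 / 30.44 = 16.8 months.
- Relative to the 2-week renal limit: 73 / 2 = 36.5 times as long.

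Group 3 starts no HCV treatment, so its Day 0 is an assumption; it is counted here on the same calendar as Groups 1 and 2.

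**Number affected.** 12 × 3 = 36 participants at most, of any sex. With two scans each, 36 × 2 = 72 scans at most. The number of women of childbearing potential among them is not stated.

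**Could another provision supply the check?**
- *Standard-of-care laboratory work.* Section 6 leaves this to site practice, and nothing names a pregnancy test within it. Appendix B marks HCV standard-of-care labs at screening, end of treatment and week 24 only, and only for the two HCV groups. Even if a pregnancy test were part of that panel, the last one would be 72 - 24 = 48 weeks before the second scan, and Group 3 would have none from this source. Section 9 counts cardiac imaging as a study intervention, not routine care.
- *Contraception.* The commitment in section 3.2 applies to "Women of childbearing potential who receive ribavirin". It covers neither women on ribavirin-free regimens nor HIV mono-infected women, and it is not a test.
- *Section 10.* It acts once a pregnancy is known.

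None of these places a pregnancy check near either scan.

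**The case against.** **A test does come before the first scan.** A reader might infer that neither scan is preceded by any pregnancy test. The documents do not support that: the screening test is mandatory and the first MRI follows it. Only a maximum interval is missing there. The week-72 scan is the larger gap, because no repeat test is specified.

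**MRI eligibility may be judged afresh at each scan.** Section 4.3 bars breastfeeding women from the study, yet Appendix C would scan a lactating woman who agrees to discard milk for 24 hours. This suggests that Appendix C may be applied as its own checklist, with pregnancy and lactation asked about on the day. The reading is reasonable, and the protocol nowhere says that the week-72 scan relies on the screening result. But the clause names no test, and asking does not detect an unrecognised pregnancy.

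**The NIH may already do this.** All scans take place there under a separate NIH consent (sections 6, 7.1 and 14.1) that is not among the reviewed documents. A pre-scan test could be required in that consent or in imaging-site procedure. This stands. A reader might infer that pregnant women will in practice be scanned; the documents show only that the protocol is silent.

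**The screening result might be older still.** Section 6.1 accepts outside labs up to 6 months old for eligibility. A reader might add those months to the interval. The text does not say that the allowance covers pregnancy tests, and the next sentence calls for a test at the screening visit, so nothing is added here.

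**The consequence is limited.** Pregnancy is excluded at entry, tested at screening, excluded again for MRI and grounds for discontinuation. The gap is one unwritten step in an optional exploratory component. That limits the weight of the point but does not remove it, because the step is cheap and the protocol sets a comparable one for renal function.

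**Conclusion.** The point holds for the written protocol. The only specified pregnancy test is at screening. The Day -7 MRI follows that test with no stated maximum interval. The week-72 MRI follows it by at least 73 weeks (511 days) on the nominal schedule, with no repeat specified. Appendix C excludes pregnant women from both scans but sets a verification window only for renal function.

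This is a worthwhile low-cost improvement to participant safety, and it has no bearing on the hsCRP endpoint, the power statement or any analysis. It rests on screening falling on or before Day -7 and on Group 3 sharing the same calendar. Confidence is high that the reviewed text is silent. Whether the gap exists in practice depends on NIH imaging procedures that cannot be seen here.

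**What to change.** **Appendix C.** Require a negative pregnancy test for women of childbearing potential in all three groups on the day of each MRI, or within a short fixed window, with the result available before gadolinium is given. If the test is positive, cancel the scan and apply section 10.

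**Appendix B.** Add a pregnancy-test row at Day -7 and week 72 for all three groups, limited to women of childbearing potential who have the MRI.

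**Alternative.** If the NIH consent or imaging-site procedure already requires this, cite it in Appendix C.

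**Cost.** At most 36 × 2 = 72 inexpensive tests, and that only if every MRI participant were a woman of childbearing potential. They would be done at visits already scheduled, with an amendment to two appendices. A few scans might be cancelled, which would lose some paired exploratory MRI data.

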6.2 Interim Visit

Up to 36 patients (12 from each group) will have a cardiac MRI performed at the NIH after screening but before Day 0 (the start of HCV treatment). See Appendix C for MRI procedure and specific inclusion and exclusion criteria.

6.3 Standard of care HCV treatment

All participants with HCV will be started on HCV treatment on Day 0 after confirming eligibility. Patients will complete visits and laboratory monitoring as per standard of care guidelines.

